8.3 Management Options for Hematologic Adverse Events

Neutropenia	
Grade 1 (ANC < 1500 to < LLN)	Maintain dose level

Grade 2 (ANC 1000 to < 1500)	Maintain dose level
Grade 3 (ANC 500 to < 1000)	Hold therapy until resolved to \leq grade 2, then:
	If resolved in ≤ 7 days, maintain dose level
	If resolved in > 7 days, reduce by 1 dose level
Grade 4 (ANC < 500 or febrile neutropenia)	Hold therapy until resolved to \leq grade 2, then
	restart at one dose level lower.
Thrombocytopenia	
Grade 1 (PLT 750000 to < LLN)	Maintain dose level
Grade 2 (PLT 50000 to < 75000)	Hold therapy until resolved to \leq grade 1, then:
	If resolved in ≤ 7 days, maintain dose level
	If resolved in > 7 days, reduce by 1 dose level
Grade 3 (PLT 25000 to < 50000)	Hold therapy until resolved to \leq grade 1, then
Grade 4 (PLT < 25000)	restart at one dose level lower.

9. ADVERSE EVENTS: LIST AND REPORTING REQUIREMENTS

9.1 Adverse events

A summary list of reported treatment-related treatment-emergent adverse events for MGCD516 is provided below. For a detailed list of all treatment emergent adverse events reported in the phase 1 trial of MGCD516 in solid tumors, please see section 3.2. Based on the most recently available information the phase 1/1b study (as of 7/2016 and representing 61 patients treated with the drug), the following treatment-related treatment-emergent adverse events were reported:

Likely (>20%)	Less Likely (5-20%)	Rare but Serious (<3%)			
 Diarrhea Fatigue (feeling tired) Hypertension (high blood pressure) 	 Blood clots, in the veins or lungs Change in voice Constipation Cough Decreased appetite Dry mouth Low thyroid level (hypothyroidism) Nausea Mucosal inflammation and/or irritation, including mouth pain Rash Swelling and/or redness and/or pain of the hands and feet Vomiting Weakness Weight loss 	 Decrease in heart function or heart pumping Fever with low white blood cells (infection fighting cells) Increase in pancreas-related enzymes Increase in heart rate (tachycardia) Increase in liver function tests (possible liver damage) Protein in the urine Weakness, numbness and/or pain due to nerve injury (neuropathy) 			

MGCD516 is a small molecule multi-receptor tyrosine kinase inhibitor of a range of RTKs. As such, it may share some similar properties with other small molecule RTK inhibitors, although adverse events associated with the drugs are likely to vary based on the particular RTKs selectively inhibited.

9.2 Definitions

Adverse Event: An adverse event (AE) is any untoward or unfavorable medical occurrence in a human subject, including abnormal sign, symptom or disease, temporally associated with the subject's participation in research, whether or not considered related to the subject's participation in the research. Abnormal results of diagnostic procedures are considered to be adverse events if the abnormality, results in study withdrawal, is associated with a serious adverse event, is

associated with clinical signs or symptoms, leads to additional treatment or to further diagnostic tests, is considered by the investigator to be of clinical significance

Serious Adverse Event: Adverse events are classified as serious or non-serious. A serious adverse event is any AE that is:

- fatal
- life-threatening
- requires inpatient hospitalization/prolongation of existing hospitalization, unless: (1) routine treatment or monitoring of the studied indication, not associated with any deterioration in condition (procedures such as central line placements, paracentesis, pain control); (2) elective or pre-planned treatment for a pre-existing condition that is unrelated to the indication under study and has not worsened since the start of study drug; (3) treatment on an emergency outpatient basis for an event not fulfilling any of the definitions of an SAE given above/below and not resulting in hospital administrations; (4) social reasons and respite care in the absence of any deterioration in the patient's general condition
- results in persistent or significant disability or incapacity
- a congenital anomaly or birth defect
- an important medical event. An important medical event is one that may not be immediately life threatening but is clearly of major clinical significance. It may jeopardize the subject, and may require intervention to prevent one of the other serious outcomes noted above. For example, drug overdose or abuse, a seizure that did not result in inpatient hospitalization, or intensive treatment of bronchospasm in an emergency department would all typically be considered serious.

Unanticipated Problem: An unanticipated problem is any incident, experience or outcome involving risks to subjects or others in any human subjects research that meets all of the following criteria:

- unexpected (in terms of nature, severity or frequency) given (a) the research procedures that are described in the IRB-approval protocol and informed consent document, and (b) the characteristics of the subject population being studied:
- related or possibly related to participation in such research (e.g., there is a reasonable possibility that the incident, experience or outcome may have been caused by the procedures involved in such research); and

 suggests that the research places subjects or others at a greater risk of harm (including physical, psychological, economic or social harm) than was previously known or recognized.

Adverse Event Reporting Period: The study period during which adverse events must be reported is normally defined as the period from the initiation of any study procedures (after the first dose of study treatment) to the end of the study treatment (last dose of study treatment) and follow-up. For this study, the study treatment follow-up period is defined as 28 days following the last administration of study treatment.

Baseline/Preexisting Condition: A baseline/preexisting condition is one that is present at the start of the study. A preexisting condition should be recorded as an adverse event if the frequency, intensity, or if the character of the condition worsens during the study period.

General Physical Examination Findings: At screening, any clinically significant abnormality should be recorded as a preexisting condition. At the end of the study, any new clinically significant findings/abnormalities that meet the definition of an adverse event must also be recorded and documented as an adverse event.

Post-study Adverse Event: All unresolved adverse events should be followed by the investigator until the events are resolved, the subject is lost to follow-up, or the adverse event is otherwise explained. At the last scheduled visit, the investigator should instruct each subject to report any subsequent event(s) that the subject, or the subject's personal physician, believes might reasonably be related to participation in this study.

Abnormal Laboratory Values: A clinical laboratory abnormality should be documented as an adverse event if any one of the following conditions is met:

- The laboratory abnormality is not otherwise refuted by a repeat test to confirm the abnormality
- The abnormality suggests a disease and/or organ toxicity
- The abnormality is of a degree that requires active management (e.g., change of dose, discontinuation of the drug, more frequent follow-up assessments, further diagnostic investigation, etc.).

Hospitalization, Prolonged Hospitalization or Surgery: Any adverse event that results in hospitalization or prolongation of hospitalization should be documented and reported as a serious adverse event unless specifically instructed otherwise in this protocol. Any condition responsible for surgery should be documented as an adverse event if the condition meets the criteria for an adverse event.

Neither the condition, hospitalization, prolonged hospitalization, nor surgery are reported as an adverse event in the following circumstances:

• Hospitalization or prolonged hospitalization for diagnostic or elective surgical procedures for a preexisting condition. Surgery should **not** be reported as an

outcome of an adverse event if the purpose of the surgery was elective or diagnostic and the outcome was uneventful.

- Hospitalization or prolonged hospitalization required to allow efficacy measurement for the study.
- Hospitalization or prolonged hospitalization for therapy of the target disease of the study, unless it is a worsening or increase in frequency of hospital admissions as judged by the clinical investigator.

9.3 Recording of Adverse Events

Signs or symptoms of the patient's cancer diagnosis and/or comorbidities at baseline will be recorded beginning on day 1. At each contact with the subject, the investigator must seek information on adverse events by specific questioning and, as appropriate, by examination. Assessment of adverse events will include type, incidence, severity (as graded by CTCAE version 4), timing, seriousness, and relatedness to study treatment. For each adverse event, the investigator will determine and document whether there exists a reasonable possibility that the study drug treatment caused or contributed to the adverse event. When the investigator does not know whether or not the study treatment is causally-related to the event, reporting for study purposes will be as "related" to study treatment.

Information on all adverse events should be recorded immediately in the source document, and also in the appropriate adverse event module of the case report form (CRF). All clearly related signs, symptoms, and abnormal diagnostic procedures results should recorded in the source document, though should be grouped under one diagnosis.

All adverse events occurring during the study period must be recorded. The clinical course of each event should be followed until resolution, stabilization, or until it has been determined that the study treatment or participation is not the cause. Serious adverse events that are still ongoing at the end of the study period must be followed to determine the final outcome. Any serious adverse event that occurs after the study period and is considered to be possibly related to the study treatment or study participation should be recorded and reported immediately.

9.4 Reporting of Serious Adverse Events

9.4.1 IRB Notification by Sponsor-Investigator

Reports of all events (including follow-up information) that meet the definition of an unanticipated problem posing risk to subjects or others must be submitted to the IRB within one week (5 business days) following the occurrence of the unanticipated problem or the principal investigator's acquiring knowledge of the unanticipated problem in accordance with IRB policy. Additionally, the sponsor-investigator will submit a summary of all unanticipated problems that occurred since the beginning of the study at the time of continuing review. Copies of each report and documentation of IRB notification and receipt will be kept in the Regulatory binder.

9.4.2 FDA Notification by Sponsor-Investigator

Columbia University Medical Center will be responsible for all communication with the FDA. Columbia University Medical Center will report to the FDA, regardless of the site of occurrence, any adverse event that is serious, unexpected and for which there is evidence to suggest a causal relationship between the drug and the adverse event. These must be reported to the FDA and any affiliate sites as soon as possible, but in no case later than 15 calendar days after the sponsor determines that the information qualifies for reporting. Columbia University Medical Center will also submit an IND annual report to the FDA in accordance with 21.CFR 312.33.

Columbia University Medical Center must report to the FDA and any affiliate site investigators as follows:

- Any unexpected fatal or life-threatening event must be reported as soon as possible, but no later than 7 calendar days after the sponsor investigator initial receipt of the information
- Any findings from epidemiological studies, pooled analysis of multiple studies, or clinical studies, whether or not conducted under an IND, and whether or not conducted by the sponsor-investigator, that suggest a significant risk in humans exposed to the drug must be reported as soon as possible but no later than 15 calendar days after the sponsor-investigator determines that the information qualifies for reporting
- Any findings from animal or in vitro testing whether or not conducted under an IND, and whether or not conducted by the sponsor-investigator, that suggest a significant risk in humans exposed to the drug must be reported as soon as possible but no later than 15 calendar days after the sponsor-investigator determines that the information qualifies for reporting
- Any clinically important increase in the rate of a serious suspected adverse reactions over that listed in the protocol or Investigator Brochure
- Expected SAEs and AEs will be included in the IND Annual Reports.

Follow-up information to a safety report should be submitted as soon as the relevant information is available. However, if the results of a sponsor's investigation show that an adverse drug experience not initially determined to be reportable are so reportable, the sponsor investigator must report such experience as soon as possible, but no later than 15 calendar days after the determination is made.

All other serious unexpected experiences associated with the use of the study treatment will be reported to FDA as soon as possible but in no event later than 15 calendar days after initial receipt of the information.

9.4.3 DSMC Reporting by the Sponsor Investigator

Serious adverse events not constituting unanticipated problems are to be reported to the HICCC DSMC. Reporting should occur within 24 hours of knowledge of the SAE occurring at our institution or affiliate sites.

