12.9 Stopping Rules

Adverse event stopping rule: Accrual will be temporarily suspended to this study if (a) at any time, 2 patients have experienced a grade 5 event considered at least possibly related to the study treatment and not related to disease progression or (b) more than 40% of all patients, when accrual is equal to or greater than 10 patients, have experienced a grade 3 or higher adverse event. In addition, each grade 5 event will be reviewed at the time of occurrence to determine whether study accrual should be suspended to protect the safety of patients. This adverse event stopping rule may be altered in the event of the study reopening after a temporary suspension or should new information become available related to the safety of the study drug.

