14.3 Data and Safety Monitoring Committee

The NCI-approved Data Safety and Monitoring Committee (DSMC) of the Herbert Irving Comprehensive Cancer Center (HICCC) will monitor every subject who receives treatment on this protocol for toxicity. This protocol will adhere to the policies of the currently approved HICCC Data and Safety Monitoring Plan (DSMP), which is in accordance with NCI and CUMC-IRB policy and guidelines. The committee is chair is appointed by the HICCC Director. The committee consists of HICCC faculty and staff with expertise in oncology, research pharmacy, research nursing, and data management. The DSMC convenes twice a month to review patient safety and the conduct of the trial. The PI will submit data and safety monitoring reports to the DSMC at a frequency to be determined by the DSMC based on risk to the subjects.

At the time of renewal, the study team will submit the most recent DSMC approval letter for safety review to the CUMC IRB. Any modifications that are required by the DSMC to ensure patient safety will be submitted to the IRB. All protocol deviations, violations, and eligibility waivers will be submitted to and approved by the DSMC prior to being reported to the IRB. All study data reviewed and discussed during these meetings will be kept confidential.

For multicenter research, the principal investigator will assure that there is a mechanism in place to distribute the report to all participating investigators for submission to their local IRB. The report will document that a review of data and outcomes across all centers took place on a given date. It will summarize the DSMC's review of the cumulative toxicities reported from all participating sites without specific disclosure by treatment arm. It will also inform site investigators of the study the DSMC's conclusion with respect to progress or need for modification of the protocol.

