Follow-up information is sent to the same person to whom the original SAE Report Form was sent, using a new SAE Report Form stating that this is a follow-up to the previously reported SAE and giving the date of the original report. Each re-occurrence, complication, or progression of the original event should be reported as a follow-up to that event regardless of when it occurs. The follow-up information should describe whether the event has resolved or continues, if and how it was treated, and whether the subject **continued** or withdrew from study participation or if study drug was interrupted or discontinued.

If the SAE is not previously documented in the Investigator's Brochure for the study drug (new occurrence) and is thought to be related to the investigational agent, the sponsor-investigator may urgently require further information from the investigator for reporting to Health Authorities.

Non-Serious Adverse Event Reporting: Non-serious adverse events will be reported to the Columbia University Medical Center Overall Principal Investigator on the toxicity Case Report Forms.

Reporting to the Institutional Review Board (IRB) and the Data and Safety Monitoring Committee: All Unanticipated Problems (UPs) will be reported to the CUMC IRB. SAEs not constituting UPs will reported to the HICCC DSMC. Each affiliate site will be responsible for safety reporting to their local IRB. Investigators are responsible for complying with their local IRB's reporting requirements, though must submit the required reports to their IRB no later than 7 calendar days following the occurrence of the UP or the Principal's Investigator's acquiring knowledge of the UP. Copies of each report and documentation of IRB notification and receipt must be included in the regulatory binder. Expected or unexpected AEs must be reported at the time of continuing review of a protocol.

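### Serious adverse events that are unanticipated problems are excluded from the 24-hour report to the DSMC, and no deadline is set for telling the DSMC of them

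*Combined protocol and SAP*

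**What the plan says.** Section 9.4.3 defines the sponsor-investigator's report to the DSMC by exclusion: "Serious adverse events not constituting unanticipated problems are to be reported to the HICCC DSMC". Its deadline follows: "Reporting should occur within 24 hours of knowledge of the SAE occurring at our institution or affiliate sites".

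Section 19.9, written for the affiliate sites, makes the same division, without repeating the 24 hours: "All Unanticipated Problems (UPs) will be reported to the CUMC IRB", and "SAEs not constituting UPs will reported to the HICCC DSMC".

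For unanticipated problems (UPs), section 9.4.1 says that reports "must be submitted to the IRB within one week (5 business days) following the occurrence of the unanticipated problem", or after the principal investigator learns of it. The IRB is the recipient; the DSMC is not named.

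Section 9.2 sets three criteria for a UP, all of which must be met: it is unexpected in nature, severity or frequency; it is related or possibly related to taking part; and it suggests more risk than was previously recognised.

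Section 14.3 gives the DSMC the task of monitoring every treated subject for toxicity and states: "The DSMC convenes twice a month to review patient safety and the conduct of the trial". It also has the principal investigator send safety reports at an interval that the DSMC chooses. Under section 14.4 the Compliance Coordinator summarises both SAEs and UPs for the committee at its regular meetings.

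Section 12.9 suspends accrual after two grade 5 events that are at least possibly related, and adds that "each grade 5 event will be reviewed at the time of occurrence to determine whether study accrual should be suspended". It does not say who does the reviewing.

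**The concern.** The exclusion runs against the purpose of expedited reporting. A serious event that meets all three UP criteria tells a toxicity monitor more than most others, yet it is the class removed from the 24-hour report. A serious event that is expected, or is unrelated to treatment, reaches the committee within a day. One that is unexpected, possibly related and points to new risk has no stated time limit.

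The wording appears in two sections, so it is unlikely to be a slip, and staff at the coordinating center and the affiliates would follow it as written. What is at stake is how soon the committee that oversees toxicity learns of such events in a small single-arm trial whose first stage has 13 patients. No endpoint, error rate or analysis is affected.

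**Working it through.** The plan states no figure for this delay, so the check sets the routes side by side and then sizes the gap.

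**Who is told, and when**

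| Recipient | Event | Stated limit | Section |
|---|---|---|---|
| DSMC | SAE that is not a UP | 24 hours | 9.4.3 |
| DSMC | SAE that is a UP | none stated | 9.4.3, 19.9 |
| IRB (coordinating center) | UP | 5 business days | 9.4.1 |
| FDA and affiliate investigators | unexpected fatal or life-threatening event | 7 calendar days | 9.4.2 |
| Manufacturer | fatal or life-threatening SUSAR | 5 calendar days | 9.4.4 |
| Overall principal investigator | every SAE at an affiliate site | 24 hours | 19.9 |

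Of these recipients, only the DSMC has no stated limit for an unexpected, possibly related death that is a UP.

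**Routes by which a UP does reach the DSMC.** There are two: the Compliance Coordinator's summary at scheduled meetings (14.4), and the principal investigator's reports at the DSMC's chosen frequency (14.3). Neither is tied to the date of an event.

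**Delay through the meeting summary.** Inputs: two meetings a month (14.3). Assumptions: a 30-day month, even spacing, and an event ready for the next summary.
- Longest wait: 30 / 2 = 15 days.
- Average wait for an event at a random time: 15 / 2 = 7.5 days.

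**Enrolment during the wait.** Input: 2-3 patients per month (15.2).
- Longest wait: (15 / 30) × 2 = 1.0 to (15 / 30) × 3 = 1.5 patients.
- Average wait: (7.5 / 30) × 2 = 0.5 to (7.5 / 30) × 3 = 0.75 patients.

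**Which events are affected.** Limb (a) of 12.9 counts grade 5 events that are at least possibly related (and not related to disease progression). The exclusion in 9.4.3 also needs unexpectedness and a suggestion of greater risk. So a possibly related death judged expected, or judged not to suggest added risk, still goes to the DSMC within 24 hours. A possibly related death could well meet all three criteria: the adverse event list in 9.1 names no fatal outcome, and 9.3 has events of unknown cause reported as related. The documents do not make that classification certain.

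**The case against.** The strongest reply is that oversight does not rest on this one report. Affiliate sites send every SAE, UP or not, to the overall principal investigator within 24 hours, and all patients are registered centrally. The sponsor-investigator can therefore review each death and apply the suspension rule without waiting for the committee. The IRB, FDA and manufacturer have their own deadlines. The DSMC can ask for investigator reports as often as it likes, so 15 days is not a fixed delay. The protocol also binds the trial to an institutional monitoring plan that is not reproduced, and section 14.4 has compliance staff check that SAEs and UPs were reported as the DSMC requires. That plan may already call for prompt UP reports.

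Most of this stands, and it rules out three stronger readings that a reader might draw:

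- **That the DSMC is never told of UPs.** The meeting summaries in 14.4 expressly cover them.
- **That the suspension rule in 12.9 would fail, or that accrual would run on past its trigger.** The rule neither names the DSMC as reviewer nor makes suspension wait for its notice, and a single related death does not trigger limb (a).
- **That every drug-related death is held back, or that only expected events are expedited.** A death is excluded only if it meets all three UP criteria, and the 24-hour group also includes unexpected events that are unrelated.

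What the reply does not remove is the exclusion itself. Notice to the principal investigator is not notice to the monitoring committee. If the institutional plan does require UP reports to the DSMC, then 9.4.3 and 19.9 misstate that duty and still need correcting.

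**Conclusion.** The point holds as a gap in the timing of notice. Under the protocol's text, SAEs that are unanticipated problems can reach the DSMC later than other SAEs, because they are taken out of the expedited report and nothing replaces it. The size is modest and is a worst case rather than an expectation. It rests on the spacing and readiness assumptions above, on accrual at the planned rate, and on the institutional plan adding nothing. More frequent investigator reports would shorten the wait; an event that missed a summary would lengthen it. An amendment is worthwhile because the ordering of notice is the reverse of what a toxicity monitor needs and costs little to put right.

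**What to change.** - **9.4.3 and 19.9:** delete the qualifying phrase that leaves out unanticipated problems, so that every SAE goes to the DSMC within 24 hours of knowledge. State that an SAE which is also a UP goes to the IRB as well, within the 5 business days already set in 9.4.1.
- **12.9:** reconcile with these sections by stating who reviews each grade 5 event.
- **Check against the institutional monitoring plan,** so that the protocol and the plan give the same duty.

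The cost is wording in three sections and one additional DSMC report per affected event, on the committee's SAE form already listed in 9.5. Affiliate sites need no new step, since they already send every SAE to the overall principal investigator within 24 hours. No threshold, dose or analysis changes.
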